Intervention arms and procedures. All women will be mailed a SHE-Women booklet with the intervention content. Electronic women's health literacy intervention procedures (intervention arm). e will deliver the integrated, multimedia electronic women's health literacy intervention arm of SHE-Women in text-Web format for individuals recently released from jail or have recent involvement with the criminal-legal system (2 years). Two health educators will be responsible for delivering content to participants, with an estimated contact time of ~10 hours pushed to participants over approximately a 5-day period. However, because it is a text-Web intervention, accessing content will be dependent on user engagement with the platform. We will measure uptake of the intervention components as it relates to number of minutes of engagement and length of time (total number of days) that all content was accessed. The lead health educator will describe the study and obtain consent from participants. If participants consent, they will immediately be asked to participate in a baseline survey.

For Aim 1 pilot study participants, this will occur over phone or in person in the community. For Aim 2 RCT participants – all of this will occur at the jail at the participant's time of discharge. Participants will be informed that after consent/ after they leave jail, in order to initiate the program, they should contact the health educator through phone, text message, email, or Facebook message. We estimate that we might lose 30% of women between consent and initiation of the community-based intervention, simply because they do not follow-up with us. Thus, in the Aim 1 pilot study we will over-recruit by 15 women; and in the Aim 2 RCT we will over recruit by 60 women, to make up for potential loss to attrition. To improve rates of follow-up, we will also collect multiple points of expected contact information for the participants: phone numbers, addresses for themselves or family members; usual places of hangout; and Facebook handle. That way, if participants don't reach out to us within three days of consent/release from jail, we can contact them.

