Power. The sample size for the Aim 1 feasibility study is based on our original SHE study pilot and expanded to allow for rigorous testing and refining of modality.²⁶ The sample size of N~200 for the Aim 2 RCT was determined to provide satisfactory power ($\geq 80\%$) for this study in addressing the specific aims, which depends on the following parameters: number of participants (n), number of measurements (t=3 for health literacy for screening; t=4 for screening/risk reduction practices), effect size (f) as group difference in change, correlation between repeated measures (r), and attrition rate. The effect sizes estimated from the original SHE study were in the small to moderate range—for health literacy (8 domains), average $f=0.13$ at immediately post-intervention and 0.16 at 1-year post-intervention; $f=0.17$ for cervix screening and 0.12 for condom use during the last intercourse at 1-year post-intervention. Although effect sizes for breast cancer screening and STI screening are not available from the original SHE study, we expect similar, small to moderate effect sizes for these outcomes. Thus, we conservatively assumed the smallest observed effect size of $f=0.12$ for our power calculation. The correlations between repeated measures observed in the original SHE study were $r=0.46$ on average, with the range of 0.39-0.75 between baseline and immediately post-intervention and 0.25-0.61 between baseline and 1-year post-intervention. Power analysis of these data ($f=0.13$, $t=3$ or 4, $r=0.46$) and G*Power 3.1.9.2 indicated that a sample of 124 women will produce $\geq 80\%$ power for both health literacy (80%) and screening/risk reduction behaviors (85%). In our original SHE study, the 3-year follow-up rate was 85%. Conservatively assuming a high attrition rate up to 40%, we will recruit ~200 women at baseline to adequately power the SHE-Women study—i.e., maintain $\geq 80\%$ power even with a low follow-up rate as small as 60%. As

Table 4. Expected attrition over study period

	Aim 1 feasibility Target N~20	Aim 2 RCT Target N~200	Aim 3 (same as Aim 2)
Consent and baseline	20	260	--
Intervention initiation	15	220	--
Post-intervention	10	200	--
1 year follow-up	--	170	--
2-year follow-up	--	160	--
3-year follow-up	--	150	--

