described above, missing data due to either attrition or nonresponse will be fully recovered via multiple imputation in our intent-to-treat analysis, which will provide additional power and remove any confounding effect of missing data on our statistical power. For Aim 3, the key stakeholder interviews will occur with enough research participants to reach thematic saturation. Based on prior experience with key stakeholder interviews, we believe N~20 interviews will accomplish this goal,²⁷ but have resources to interview additional participants. Additionally, our COVID-19 module interview suggests N~30 interviews will accomplish the goal of thematic saturation.

Outcomes and instruments. Aim 1 feasibility outcomes include uptake of intervention components, barriers and facilitators of implementation, problems with delivery, and necessary modifications.⁴⁵ Pilot effectiveness outcomes will include an assessment of women's health literacy, operationalized as knowledge, beliefs, and self-efficacy for screening related to cervical, breast cancer, birth control, and STIs, post-intervention.^{4,26} Aim 2 RCT outcomes include women's health literacy, immediately post-intervention and 1-year post-intervention; and screening/ risk reduction for cervical, breast cancer, unintended pregnancy, and STIs at 1, 2, and 3-years post-intervention. Aim 3 outcomes include perception and uptake of intervention components.⁴⁵

Feasibility and perception of intervention outcomes are defined below and assessed through participant tracking and key stakeholder interviews with a subset of participants.:

- *Uptake of integrated, multimedia electronic women's health literacy intervention:* documentation of number of participants who responded to text messages; clicks on Website; real-time assessment of knowledge; time elapsed between text messages and Website clicks; number of outreach messages (through text, phone, or Facebook); Facebook posts/messages; chats with health educator; total minutes of contact through text, Web, chat, Facebook with each participant; attendance at community sessions
- *Barriers and facilitators of implementation:* problems described by participants in setting up text message platform, Website, closed Facebook group; factors that make set up of text message platform, Website, closed Facebook group ease of use; ease of Website components use (content modules, assessments)

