
Missing data will be handled by iterative Markov Chain Monte Carlo (MCMC) multiple imputation, in which expectation-maximization (EM) algorithm provides prior estimates of missing values for subsequent MCMC procedure.⁶⁰ A large number of (e.g., 200) imputed datasets will be generated and then analysis results from each imputed dataset will be combined together to make valid statistical inference. This approach includes all selected variables (auxiliary variables) into the imputation process, which allows for greater recovery of missing data.⁶¹ It is possible that some women will reenter the jail facility during the recruitment period. To avoid re-randomizing these same participants, we will collect basic identifying information recruitment (name, DOB, race) and double check to see if the participant already is enrolled in our study.

Integration of study aims to meet project objective. Because the objective of this study is to ultimately create a sustainable model for dissemination of health promotion interventions for vulnerable populations, we feel it is important to use a mixed methods approach to understand the relationship between qualitative and quantitative data.⁶² Integration of study aims to meet our project objective will primarily occur through the writing of Manuscripts # 1,6 and 8 (see Table 3). In each of these manuscripts we plan to report on both the perceptions of key stakeholders, as well as the effectiveness of the intervention given the electronic modality of delivery. We will take lessons learned to develop subsequent projects that test SHE-Women in diverse groups of high risk women both inside and outside our catchment area.

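### Intervention women who never start have no stated route to the post-intervention assessment, so imputation by arm would move the intent-to-treat literacy effect toward the effect in users

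*Combined protocol and SAP*

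**What the plan says.** **Randomisation and early loss.** The control-arm section has women randomised once they have consented. Under Intervention arms and procedures, a woman must then get in touch with the health educator to begin. That section says "We estimate that we might lose 30% of women between consent and initiation of the community-based intervention" and "in the Aim 2 RCT we will over recruit by 60 women, to make up for potential loss to attrition". The control-arm section expects a similar 30% loss of its own. Table 4 gives, with the RCT figure last in each row, "Consent and baseline 20 260", "Intervention initiation 15 220" and "Post-intervention 10 200". It does not split these by arm.

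**Who is assessed.** In the intervention arm, the daily prompts and the Day 5 invitation to the assessment go to women who have initiated. The other trigger is that a woman has opened all the content, for which she has three weeks. Staff may contact a woman who has not been in touch within three days, but the text does not say that this leads to an assessment. Controls are contacted for theirs after five days.

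**What both arms receive.** "All women will be mailed a SHE-Women booklet with the intervention content". Texting with a health educator and the library sessions are also open to both arms.

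**Missing data.** Data analysis says "Missing data will be handled by iterative Markov Chain Monte Carlo (MCMC) multiple imputation", with a large number of imputed datasets (200 as the example) and auxiliary variables that are not listed. Power says "missing data due to either attrition or nonresponse will be fully recovered via multiple imputation in our intent-to-treat analysis", and adds that this increases power and takes away confounding by missing data as it bears on power. No missing-at-random assumption is stated and no sensitivity analysis is planned.

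**The concern.** Whether a post-intervention literacy score exists depends on uptake in one arm and on elapsed time in the other. In the intervention arm, the observed scores come from women who started. An imputation model that contains arm has only those scores from which to learn what an intervention woman's post-intervention score looks like. It therefore gives never-starters the expected scores of women who used the content, although what they received is close to what controls received.

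This goes beyond a general doubt about missing at random. The group is defined by the trial's own procedures, it is expected in advance, and it can be identified from the planned tracking data. At stake is the Aim 2 comparison at the first post-baseline visit: the effect among users would be reported as the effect of offering SHE-Women to women leaving jail.

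**Working it through.** **Inputs.** Table 4, RCT column: 260 at consent and baseline, 220 at initiation, 200 post-intervention. Intervention arms and procedures: 30% lost before initiation, 60 extra women. Power: average correlation between repeated measures r = 0.46. Not in the documents: h, the effect in never-starters as a fraction of the starters' effect. It is varied from 0 to 1.

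**The plan's own loss figures.** 200 × 1.30 = 260 reproduces the target. Dividing by the retained share would give 200/(1 − 0.30) = 286. A 30% loss from 260 leaves 260 × 0.70 = 182, which is below both the 220 and the 200 in Table 4. Table 4 itself implies 40/260 = 15.4% lost before initiation. The share who start, s, is therefore 220/260 = 0.846 or 0.70, depending on the section.

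**Imputation with arm in the model.** Let d be the starters' effect over control.

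- Effect of the offer: d × [s + (1 − s)h].
- With no never-starter outcome at any visit, these women are imputed with effect d, so the analysis returns d.
- Overstatement: 1/[s + (1 − s)h] − 1.

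| h | s = 0.846 | s = 0.70 |
|---|---|---|
| 0 | 1/0.846 − 1 = 18.2% | 1/0.70 − 1 = 42.9% |
| 0.5 | 1/0.923 − 1 = 8.3% | 1/0.85 − 1 = 17.6% |
| 1 | 0% | 0% |

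A simulation of regression imputation (400,000 women, r = 0.46, h = 0, illustrative d = 0.50 SD) gave 0.50 against a true 0.42 (18.1%) and 0.50 against 0.35 (43.8%).

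**Dropping never-starters.** Analysing starters alone also returns d if the two groups are otherwise alike, so the table applies unchanged.

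**Arm left out of the imputation model (h = 0).** The bias cancels when control loss equals the never-start share (simulated −0.6% and 0.9%). If all controls are observed and allocation is 1:1, never-starters are filled in at the pooled observed mean, s·d/(1 + s). The overstatement is then (1 − s)/(1 + s): 0.154/1.846 = 8.3% and 0.30/1.70 = 17.6%.

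**One-year scores observed and used (h = 0).** With the same effect at both visits and a common r, the one-year score has weight r/(1 + r) = 0.46/1.46 = 0.315, so a fraction 0.685 of the bias remains. 18.2% × 0.685 = 12.5% and 42.9% × 0.685 = 29.4%; the simulation gave 11.8% and 29.5%, so about 12% and 29%.

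**Pooled row.** If all 40 early losses were among 130 intervention women (1:1 assumed), the figure is 130/90 − 1 = 44.4%.

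**Starters who do not finish.** If the 20 women between 220 and 200 are also unassessed and gain nothing, the figure is 260/200 − 1 = 30.0%. Correcting only for women who opened nothing would leave 220/200 − 1 = 10.0%.

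**The case against.** The strongest reply is that the plan is too thinly specified to be convicted of this. The imputation variables are not listed, so arm may be absent and uptake present. The moment of randomisation is not fixed relative to the initiation contact. The recruitment text aims to end with about 200 women, so early losses may be replaced and not imputed. Literacy is measured again at one year and retention efforts are not limited to starters, so joint imputation could borrow from a never-starter's later score. A zero effect in never-starters is an assumption.

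Much of this stands as a limit on size. It does not rescue the plan:

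- Leaving arm out sits badly with the planned group-by-time test, and removes the bias only if losses happen to balance.
- Excluding never-starters gives the starters' effect under an intent-to-treat label.
- The matching 30% loss expected in the control arm implies that loss is counted by arm, and so after randomisation.
- One-year scores reduce the bias but do not remove it.

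A reader might infer that no auxiliary variable could help. The one-year score shows otherwise. A reader might also take the aim of testing effectiveness in real-life circumstances as a statement that non-initiation must be captured. In context, that sentence explains why no devices are supplied, so it is not relied on here.

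**Conclusion.** The concern holds as a defect in the design of assessment and imputation. The plan gives no route to a post-intervention score for randomised intervention women who never start, and both usual ways of handling them move the result toward the effect in users. The claim of full recovery in an intent-to-treat analysis does not hold for this group.

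A reader might infer that the effect will be overstated by 18% to 43%. The documents do not support that. Those figures are upper values that need four conditions: no gain over control in never-starters, arm in the imputation model (or never-starters dropped), no later scores, and all randomised women as the target population. The first is plausible, because the booklet, the texting and the sessions go to both arms, but it is not stated. Nor is 18% to 43% an uncertainty range: its ends are two loss figures that conflict, one of them pooled over arms. Across the inputs examined, the overstatement runs from zero to about 44%.

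**What to change.** 1. Define the intent-to-treat set as all randomised women, list the imputation variables, and delete the full-recovery claim. Reconcile the 30% loss with Table 4, and give Table 4 by arm.
2. In the imputation for post-intervention literacy, and for later visits where never-starters are unobserved, use tracked content uptake (none, partial, all) in place of randomised arm alone. Impute intervention women who opened nothing from control outcomes, given baseline and any one-year score.
3. State how unassessed partial users are handled, for example by also imputing them from controls in a sensitivity analysis. An indicator of having opened any content is not enough, because one assessment trigger is completion of all of it.
4. Keep the outcome model by randomised arm, and report the arm-based missing-at-random imputation alongside.
5. Where still possible, offer the post-assessment to every randomised intervention woman at the end of the three-week window, whatever her uptake.

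Steps 1 to 4 cost SAP wording and use tracking data already planned. Step 5 costs staff contact time. The downside is a smaller, less favourable estimate that assumes never-starters resemble controls. That assumption cannot be tested without their scores, which is why both imputations should be reported.
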